5.1.3 Study Drug Administration

Study drug will be administered by the patient orally and once daily on Days 1 through 168. Study drug should be administered at approximately the same time each morning. If a patient forgets to take study drug on a given day, they should take the next dose as normal and should not take a double dose to make up for the forgotten dose.

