3.1.3 Safety Follow-up Period

Patients will be contacted by phone for a Safety Follow-up Visit (Visit 7) approximately 4 weeks (+/- 6 days) after the end of the Treatment Period for collection of adverse events (AEs).

Study Indication

The indication for this study is early AD.

Coronavirus Disease 2019 Contingency Measures

In cases of coronavirus disease 2019 (COVID-19) limitations, it is the Investigator's responsibility to assure the safety of patients, including phone or video contact to assess the patient's well-being including any AE, collection of study samples, and clinical data as best as possible, and direct shipment of study drug to the patient, if necessary. Where available and appropriate, home health care may be considered to facilitate monitoring of safety and study continuity. Documentation of these cases and the study site's management of patients should be recorded in the Investigator

study files. In the absence of a COVID-19 impact, it is expected that Investigators and patients follow the protocol requirements as set forth.

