6.1.4 Visit 5 (Day 126 ± 6 Days)

All patients returning for Visit 5 (Day 126 ± 6 days) will undergo the following procedures:

- Fasting (~10 hours) blood sampling for clinical chemistry and hematology;
- Recording of vital signs;
- Administration of the Columbia-Suicide Severity Rating Scale (C-SSRS);
- Documentation of AEs and concomitant medications;
- Study drug compliance check; and

Patients will receive a supply of study drug with instructions on how to take it. Patients will be given an appointment to return with all used and unused study drug at Day 168 (± 6 days).

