6.1.6 End of Study Visit 7 (Day 198 \pm 6 Days)

Patients will be contacted by phone for a safety follow-up (Visit 7) approximately 4 weeks (±6 days) after the End of the Treatment Visit (Visit 6) for collection of AEs.

Early Termination Visit and Withdrawal Procedures

The end of the study for patients completing the study is Visit 7. For patients who are withdrawn from the study prior to completion, all procedures planned to be performed at the End of Treatment (EOT) Visit (Visit 6) will be conducted at an Early Termination Visit if possible.

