At Baseline (Visit 2), at Day 84 (Visit 4), and the End of Treatment (Day 168, Visit 6), the following parameters will be measured in the plasma:

- Tau and p-Tau epitopes
- $A\beta_{1-42}$, $A\beta_{1-40}$, $A\beta_{1-42}/A\beta_{1-40}$ ratio
- Neurofilament light

Correlation Between the Change From Baseline Levels in CSF p-Tau 181 and CSF ApoA-I, ApoE, and Cholesterol Efflux Capacity

At Screening (Visit 1) and at the End of Treatment (Day 168, Visit 6), p-Tau 181, ApoA-I, ApoE, and cholesterol efflux capacity will be measured in the CSF.

Change From Baseline Levels in 24-Hydroxycholesterol and 27-Hydroxycholesterol in CSF and Plasma

At Baseline (Visit 2), Day 84 (Visit 4), and the End of Treatment (Day 168, Visit 6), 24-hydroxycholesterol and 27-hydroxycholesterol will be measured in the CSF and plasma samples.

Note, CSF sampling for 24-hydroxycholesterol and 27-hydroxycholesterol in CSF at Day 84 (Visit 4) is optional.

Exploratory Cognition Endpoints

Disease Progression Measured With the Cognitive-Functional Composite

At Baseline (Visit 2) and the End of Treatment (Day 168, Visit 6), the CFC test will be administered to allow tracking of disease progression.

The CFC test was designed to improve the measurement of progression in early dementia stages of AD by providing a short and clinically relevant measure focusing on the cognitive domains and activities of daily living that are sensitive to decline in early AD.

The CFC combines the Short Version of the Amsterdam Instrumental Activities of Daily Living Questionnaire (A-IADL-Q-SV) and a brief neuropsychological test battery focusing on episodic memory and executive functions^{29,30}. The psychometric quality of the CFC was evaluated in the Catch-Cog study; an international, multi-center, independent longitudinal validation study including individuals with MCI and mild dementia due to AD²⁹. The CFC was found to have good test-rest reliability, and patients and caregivers experienced the content of the CFC as relevant and the administration as user-friendly^{30,31}. Further, it was shown that the CFC has good construct validity and quality for the target population, as evidenced by associations with clinical and biological measures of disease severity^{32,33}, and limited range restrictions in scoring at baseline³³.

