APPENDIX A: SCHEDULE OF PROCEDURES

Study period	Screening	Treatment Period					Follow-
		Baseline				EOT/ET9	Up ■ (V7)
		(V2)	V3	V4	V5	(V6)	
Day (±Visit Window)	1-8 weeks	D1	D42	D84	D126	D168	D198
			±6d	±6d	±6d	±6d	±6d
Informed consent ¹	X						
Inclusion/exclusion criteria	X	X					
Demographic data	X						
Medical history and							
baseline conditions	X						
C-SSRS		X	Х	X	X	X	
Height and weight ²	X					X	
Vital signs ³	X	X	X	X	X	X	
ECG ⁴	X					X	
FSH test ⁵	X						
Urine pregnancy test ⁵	X					X	
Hematology, chemistry							
and urinalysis	X	X^6	X^7	X ⁶	X7	X	
HbA1c	X	1					
Thyroid function	X						
Folic acid and vitamin B12							
levels	X						
APOE E4 testing	X						
MRI-cerebrum ¹¹	X						
Physical examination	X	X		X		X	
Neurological examination	X	X		X		X	
Prior and concomitant	71	1		11		- 11	
medications	X	x	х	x	x	X	
Dispense study drug	71	X	X	X	X	- 11	
Study drug administration ⁸		X	X	X	X	X	
Study drug compliance		1	21	11	1	- 11	
check			X	X	X	X	
Adverse events	X	X	X	X	X	X	X
CDR	X	1		1			- 11
MMSE	X	X		X		X	
CFC	21	X		1		X	
Plasma sample for PD and				 			
PK		X		X^{12}		X^{12}	
CSF sample for PD and PK	X			X^{10}		X	

APOE E4 = apolipoprotein E-E4; CFC = Cognitive-Functional Composite; CDR = Clinical Dementia Rating; ECG = electrocardiogram; EOT = End of Treatment; ET = Early Termination; HbA1c = hemoglobin A1c; MMSE = mini-mental state examination; MRI = magnetic resonance imaging.

Note: In cases of COVID-19 limitations, it is the Investigator's responsibility to assure the safety of patients, including phone or video contact to assess the patient's well-being including any adverse event, collection of study samples and clinical data as best as possible, and direct shipment of study drug to the patient, if necessary. Where available and appropriate, home health care may be considered to facilitate monitoring of safety and study continuity. Documentation of these cases and the study site's management of patients should be recorded in the Investigator study files. In the absence of a COVID-19 impact, it is expected that Investigators and patients follow the protocol requirements as set forth.

- 1. Signed informed consent must be obtained before any study-related procedures are performed.

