- 2. Height and weight will be measured at the Screening Visit and will be used to calculate body mass index. Weight only will be measured at the EOT visit. Measurement of weight should be performed with the patient dressed in indoor clothing, with shoes removed, and bladder empty.
- 3. Vital signs will include body temperature, heart rate, and triplicate blood pressure (systolic and diastolic) measurements.
- 4. A single, standard 12-lead ECG will be performed by the Investigator or trained site personnel at the Screening Visit and at the EOT visit.
- 5. FSH test and urine pregnancy test will be performed in women <55 years of age
- 6. Only clinical chemistry panel to be performed (Appendix B)
- 7. Clinical chemistry and part of hematology (PT, PTT, INR and platelets) only (Appendix B)
- 8. Study drug will be administered by the patient orally and once daily on Days 1 through 168. Study drug should be administered at approximately the same time each morning.
- 9. Early Termination Visit only for patients who withdraw prematurely from the study.
- 10. Optional lumbar punction.
- 11. MRI is to be performed only in patients without historical MRI available within 6 months of the Screening Visit.
- 12. A single trough PK sample will be drawn on Day 84 and 168 prior to dose to measure trough levels of obicetrapib

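### Does a Visit 6 as late as Day 174 undermine the pre-dose trough when dosing is written to end on Day 168?

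*Protocol*

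**What the plan says.** - **Dosing period.** Protocol 5.1.3: "Study drug will be administered by the patient orally and once daily on Days 1 through 168". Footnote 8 of Appendix A repeats this limit.
- **Visit window.** At Visit 5 (Protocol 6.1.4) patients are "given an appointment to return with all used and unused study drug at Day 168 (± 6 days"), so Visit 6 may take place on Days 162 to 174.
- **Dose at Visit 6.** The Appendix A row "Study drug administration" is marked at Visit 6, and footnote 8 is attached to that same row.
- **PK sample.** Footnote 12, on the plasma row only: "A single trough PK sample will be drawn on Day 84 and 168 prior to dose to measure trough levels of obicetrapib".
- **Day 168 as a visit name.** Protocol 7 writes, for example, "and the End of Treatment (Day 168, Visit 6), the following parameters will be measured in the plasma". Protocol 3.1.3 times the follow-up call "after the end of the Treatment Period for collection of adverse events (AEs"), while 6.1.6 times the same call "after the End of the Treatment Visit (Visit 6) for collection of AEs". The end of treatment and Visit 6 are thus used interchangeably.
- **Early termination.** Procedures "planned to be performed at the End of Treatment (EOT) Visit (Visit 6) will be conducted at an Early Termination Visit if possible".
- **Analysis.** SAP 2.3.4 titles the PK endpoint as a steady-state level. SAP 3.5 summarises PK descriptively by visit and matrix, with no rule on time since last dose.

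**The concern.** A trough drawn before a dose presupposes that a dose is due that day and that one was taken the day before. With dosing written to stop on Day 168 and the visit allowed until Day 174, neither need be true. Samples taken off drug could then be averaged into a summary headed steady state, and SAP 3.5 has no rule to separate them. The same visit supplies the Day 168 samples for the primary pharmacodynamic endpoint, so the question seems to reach beyond an exploratory PK table. In a study of 10 to 15 patients, a single unusual value can move a mean.

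**Working it through.** **1. The plan's own figure.** 24 weeks × 7 = 168 days. Four kits (Visits 2 to 5, Protocol 5.1.2) × 6 weeks × 7 = 168 days. Both reproduce Day 168.

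**2. Day 168 read as a stop day.** Visit 6 window: 168 − 6 = 162 to 168 + 6 = 174, which is 13 days. For a sample on day *d* before any dose that day, the last planned dose day is min(*d* − 1, 168), and hours since dose = 24 × (*d* − last dose day).

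| Visit 6 day | Last planned dose | Hours since dose |
|---|---|---|
| 162–168 | day before | 24 |
| 169 | 168 | 24, but no dose follows |
| 170 | 168 | 48 |
| 171 | 168 | 72 |
| 172 | 168 | 96 |
| 173 | 168 | 120 |
| 174 | 168 | 144 |

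Five of 13 permitted days exceed one dosing interval. This counts days; it is not a probability, since the documents do not say how visits spread over the window. Visit 4 (84 ± 6 = Days 78 to 90) lies inside the dosing period and has no stop-day conflict.

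**3. Day 168 read as the name of Visit 6.** If dosing runs to the visit, the last dose is on day *d* − 1 for every *d*, the interval is 24 hours throughout, and footnote 12 is coherent.

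**4. Does drug supply settle which reading applies?** No. Kit contents beyond six weeks are not stated. Assume exactly 42 daily doses per kit and leftovers returned. The undosed days just before Visit 6 are then the Visit 5 to Visit 6 interval minus 42, or minus 43 if the new kit starts the day after Visit 5.

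- If Protocol 3.1.2 limits the gap between visits to 42 + 6 = 48 days: 6 (or 5) undosed days. Compliance on a days-elapsed denominator is 42/48 = 87.5%.
- If windows apply to nominal days, Visit 5 on Day 120 and Visit 6 on Day 174 are both allowed: 54 days, 12 (or 11) undosed days, and 42/54 = 77.8%.
- At 42 days or fewer: none.

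The result depends on the interval rule, on unstated overage and on a compliance denominator that neither document defines. One case passes the 80% per-protocol threshold and the other fails it. No firm supply figure follows.

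**5. How far could a late sample be off?** The documents give no half-life, so this is an assumed first-order range. Under the stop-day reading, a Day 174 sample is 144 − 24 = 120 hours past a 24-hour trough, and its level relative to that trough is 2^(−120/half-life).

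| Assumed half-life (h) | Day 174 level relative to 24 h trough |
|---|---|
| 24 | 3% |
| 72 | 32% |
| 120 | 50% |
| 240 | 71% |
| 336 | 78% |

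With equal troughs and one such patient among 10, the Visit 6 mean falls by (1 − 0.031)/10 = 9.7% at the shortest half-life and (1 − 0.781)/10 = 2.2% at the longest. Among 15 patients the falls are 6.5% and 1.5%.

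**6. What the plan already makes visible.** Protocol 10.1.2 requires actual sample dates and times. SAP 3.1.1 defines analysis day from first dose. SAP 6 presents all available data in participant listings, sorted by visit date where applicable. The study day of each Visit 6 sample can therefore be derived. Only the time of the last dose has no stated source, and the tablet counts in Protocol 5.1.5 give a rough bound on it.

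**The case for a change.** The best case for a change runs as follows. The change log in Protocol Appendix C says the regulator asked for exact plasma sampling times so that steady-state PK could be characterised, and footnote 12 was added to meet that request. A summary that ignores time since last dose does not fully deliver it. No sentence says that dosing continues to the actual Visit 6 date. The Visit 4 and Visit 6 procedure lists do not tell patients to hold the morning dose. Early Termination samples take the Visit 6 slot with no timing rule, and the 80% compliance threshold would pass the 48-day case.

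The ambiguity stands, and so does the absence of a dose-timing rule in SAP 3.5. The step from there to a new analysis rule does not:

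- Dosing is only approximately at the same time each morning. A cut-off at one dosing interval with no tolerance would reject a proper pre-dose sample at 24.5 hours.
- The documents do not show that a last-dose date is captured, so some samples would be unclassifiable. The eCRF, the Laboratory Manual and the separate programming specifications may cover it, but they are not available here.
- The SAP's Version 3.0 history entry cites available data points and 12 patients. Data availability was therefore already known, and an exclusion rule written now would risk after-the-fact selection in a very small descriptive table.
- The primary analysis in SAP 3.4.1 compares baseline with the Visit 6 value and does not depend on that value being a trough. It would keep all Visit 6 values under either reading.

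**Conclusion.** No change to the plan follows. This is a gap in detail that an analyst can fill sensibly: report Visit 6 PK by visit as planned, with the sample day visible in the listings. The sentences on the dosing period, the kits, the Visit 6 window, the administration mark and the pre-dose sample do need to be reconciled by the sponsor. A statement in the clinical study report of which reading was applied would do that. This review does not choose between the readings.

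The discrepancy is 48 to 144 hours since the last planned dose on Days 170 to 174 if Day 168 is a stop day, and nothing if it is the name of the visit. Its effect on the PK mean cannot be determined from the documents. The 2% to 10% illustration for one Day 174 patient among 10 rests on assumed half-lives, equal troughs and the stop-day reading. The endpoint concerned is exploratory and descriptive, no test uses it, and the primary comparison is the same either way.

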5.1.4 Treatment Compliance

Compliance to the study drug regimen will be evaluated by counting unused tablets and capsules. During the Treatment Period, if compliance is not between 80% and 120%, inclusive, the patient will be counselled about the importance of compliance to the regimen. If the limits are exceeded at 2 consecutive visits, a decision will be made by the Investigator and Sponsor as to whether the patient should be withdrawn from the study.

5.1.5 Storage and Accountability

Study drug must be stored below 25°C in a secure area with access limited to the Investigator and authorized site personnel.

In accordance with regulatory requirements, the Investigator or designated site personnel must document the amount of study drug dispensed and/or administered to patients, the amount returned by patients, and the amount received from and returned to the Sponsor (or representative) when applicable. Study drug accountability records must be maintained throughout the course of the study. Discrepancies are to be reconciled or resolved. Procedures for final disposition of unused study drug will be provided in the appropriate study manual.

Prior and Concomitant Medications and/or Procedures

5.1.6 Excluded Medications and/or Procedures

Subjects who are using any of the following medications will be excluded from participation in the study (see Section 4.2):

- Antipsychotic agents, including pimavanserin;
- Stimulant medications:
- Antidepressant medications whose dose has not been stable for at least 90 days;
- Immunosuppressant medications, including chronic corticosteroids;
- Injected or infused antibody therapies, including but not limited antibodies directed against TNF, anti-IL-6, natalizumab, rituximab and similar agents;

- Anticoagulant or anti-platelet medications including warfarin, heparinoids and direct coagulation factor inhibitors (eg, apixaban, dagibatran, rivaroxaban); either aspirin at a dose of ≤100 mg/day or clopidogrel at a dose of 75 mg/day, but not both in combination is permitted;
- Any lipid-altering therapy other than the investigational study drug.

5.1.7 Documentation of Prior and Concomitant Medication Use

Medications used within 28 days prior to the Screening Visit will be recorded. Any medications administered in addition to the study drug, whether allowed per the protocol or not, must be documented on the concomitant medication eCRF.

6 STUDY PROCEDURES

A study visit schedule in tabular format is provided in Appendix A. This study protocol includes contingency measures to manage disruptions due to COVID-19 control measures, including modifications to visit schedules and procedures specific to situations where COVID-19 is impacting study conduct. See Section 3.3 for details of COVID-19 contingency measures. In the absence of a COVID-19 impact, it is expected that Investigators and patients follow the protocol requirements as set forth.

Screening Visit (Visit 1, Week -8 to Day -1)

Patients who the Investigator considers to be appropriate for the study, will have the study explained to them and their study partner by the Investigator and will be given a dedicated copy of the written ICF. When they have had sufficient time to study this information and the opportunity to ask any questions they wish, they will be invited to give their consent to participation by signing the ICF. Signed informed consent must be obtained before any study-related procedures are performed. See Section 11.4 for details on informed consent.

Once the patients and their study partners have given consent, the following procedures will be undertaken to confirm eligibility for the study:

- Verification of inclusion and exclusion criteria;
- Confirmation of diagnosis of Stage 3 or 4 AD per NIA-AA Research Framework criteria (see Section 4.1);
 - CDR global score between \ge 0.5 and \le 1
 - MMSE score of \geq 20
- Blood sampling for APOE E4 genotyping;
- Performing MRI of cerebrum (only in patients without historical MRI available within 6 months of the Screening Visit);
- Documentation of demographics, medical history and baseline conditions;
- Recording of height and weight;
- Recording of vital signs (body temperature, heart rate, and triplicate blood pressure [systolic and diastolic]);
- Performing 12-lead ECG;
- Fasting (~10 hours) blood sampling for hematology and clinical chemistry
 - Note: HbA1c, thyroid stimulation hormone (TSH), triiodothyronine (T3), thyroxine (T4), folic acid, and vitamin B12 levels will be determined at Screening Visit only.
- Collection of urine sample for urinalysis;
- FSH and urine pregnancy test for women <55 years of age
- Physical and neurological examination;
- Documentation of prior and concomitant medication; and

• Performing of lumbar puncture for CSF sample (for inclusion and PD and PK parameters as listed in Section 7).

The MMSE must be performed at least 14 days prior to the MMSE performed at the Baseline visit to minimize learning effects.

The CDR test was designed for the staging of dementia severity. It is a 5-point scale used to characterize six domains of cognitive and functional performance applicable to AD and related dementias: Memory, Orientation, Judgment and Problem Solving, Community Affairs, Home and Hobbies, and Personal Care. The necessary information to make each rating is obtained through a semi-structured interview of the patient and a reliable informant or collateral source (eg, family member) referred to as the CDR Assessment Protocol.

Each area is rated as 0 ("healthy"), 0.5 ("questionable dementia"), 1 ("mild dementia"), 2 ("moderate dementia"), or 3 ("severe dementia").

CDR \geq 0.5 and \leq 1 (in combination with MMSE \geq 20) covers the same clinical stage in the Alzheimer's continuum as described in AD Clinical Stage 3 or 4 in the NIA-AA Research Framework.

The Screening Visit may be divided into multiple visits if more convenient for the participant.

Treatment Period – Visits 2 Through 5

6.1.1 Baseline Visit (Visit 2, Day 1)

The following procedures will be performed at Baseline (Visit 2, Day 1):

- Confirmation that the patient continues to meet the inclusion and exclusion criteria and assessing any updates since the Screening Visit;
- Recording of vital signs;
- Documentation of prior and concomitant medications;
- Documentation of AEs:
- Physical and neurological examination
- Administration of the Columbia-Suicide Severity Rating Scale (C-SSRS);
- Administration of Cognitive-Functional Composite (CFC) and MMSE;
- Fasting (~10 hours) blood sampling for clinical chemistry, and PD and PK parameters as listed in Section 7;

Patients will receive a supply of study drug with instructions on how to take it. Patients will be given an appointment to return with all used and unused study drug at Day 42 (± 6 days).

The Columbia-Suicide Severity Rating Scale (C-SSRS) is a questionnaire used for suicidality assessment. The scale will be used to determine treatment-emergent suicidal ideation and behavior.

6.1.2 Visit 3 (Day 42 ± 6 Days)

All patients returning for Visit 3 (Day 42 ± 6 days) will undergo the following procedures:

- Fasting (~10 hours) blood sampling for clinical chemistry and hematology;
- Recording of vital signs;
- Administration of the Columbia-Suicide Severity Rating Scale (C-SSRS);
- Documentation of AEs and concomitant medications;
- Study drug compliance check; and

Patients will receive a supply of study drug with instructions on how to take it. Patients will be given an appointment to return with all used and unused study drug at Day 84 (± 6 days).

